6.1 Calendar

Required studies must be done within 28 days prior to starting on the treatment.

REQUIRED STUDIES	Pre-Study	Cycle 1 +/- 2 Days				Cycle 2 +/- 2 Days				Cycle 3 ¹ +/- 2 Days				Pre-Progression Follow-Up ¹	Post-Progression Follow-Up ²
		Wk 1	Wk 2	Wk 3	Wk 4	Wk 5	Wk 6	Wk 7	Wk 8	Wk 9	Wk 10	Wk 11	Wk 12		
PHYSICAL ¹															
History and Physical Exam (informed consent)	X	X	X	X	X	X	X			X				X	X
Weight and Performance Status	X	X	X	X	X	X	X			X				X	
Toxicity Notation	X	X	X	X	X	X	X			X				X #	X #
Blood Pressure		X	X	X	X	X	X								
LABORATORY ¹															
CBC, Differential, Platelets	X	X		X		X		X		X					
CA-19-9	X									X					
Serum Chemistry ³	X	X		X		X		X		X					
U/A ⁷	X														
PT/INR	X														
X-RAYS AND SCANS ^{1, 4}															
CT/MRI for Disease Assessment ⁵	X									X				X	
EKG	X														
SPECIMEN SUBMISSION															
Blood sample (for correlatives) ⁶	X									X					
TREATMENT															
Regorafenib		X	X	X		X	X	X		X	X	X			

- 1 Protocol treatment and parameters will continue at these intervals until progression of disease or until patient has met any of the guidelines in Section 4.2.1
- 2 After off treatment following disease progression, physical assessments (with lab tests performed at the discretion of the treating investigator) should take place every 3 months for up to two years or death.
- 3 Sodium, potassium, chloride, CO₂, calcium, magnesium, phosphorus, blood urea nitrogen [BUN], creatinine, glucose, albumin, total protein, alkaline phosphatase, bilirubin [total and direct], AST, ALT

- 4 To be performed every 8 weeks until progression. Must be performed using same method as prestudy.
- 5 Scan must be performed +/- 1 week of each assessment.
- 6 Draw 1 x10mls EDTA tubes at baseline, Cycle 3 Day 1 (+/- 2 days), and at the treatment discontinuation visit if patient continues on after cycle 3 day1. (see section 13.)
7. Spot urine must not show 2+ or more protein in urine or the patient will require a repeat urine analysis. If repeat urinalysis shows 2+ protein or more, a 24- hour urine collection will be required and must show total protein excretion <3500 mg/24 hours

Toxicity should be evaluated until resolution of any adverse events.

6.2 Safety

All subjects who receive at least one dose of study treatment will be valid for the safety analysis.

All observations pertinent to the safety of the study treatment will be recorded and included in the final report.

Safety variables include the following: AEs, laboratory changes (complete blood counts, electrolytes, chemistry, and coagulation), changes in vital signs (blood pressure, heart rate, respiratory rate, and temperature) and ECG and, in some instances, changes in chest x-ray images, as produced at the investigator's discretion (e.g., for evaluation for pneumonia).

All AEs whether considered drug-related or not, will be reported with following information: start/stop dates, action taken, whether treatment was discontinued, any corrective measures taken, outcome, and other possible causes. For all events, the relationship to treatment and the intensity of the event will be determined by the investigator.

This trial will use the NCI-CTCAE v4.0 criteria for assessment of toxicity and SAE reporting with regard to toxicity grade.

6.2.1 Adverse events

Investigators should refer to the Safety Information section of the current IB for regorafenib, including the DCSI (development core safety information), for the expected side effects of, regorafenib. As with any agent, there is always the potential for unexpected AEs, including hypersensitivity reactions. The IB will be updated if any new relevant safety data are obtained.

Therapeutic monitoring should be performed following dose selection or modification of regorafenib, in a manner consistent with the local clinical standard of care. In general, subjects should be closely monitored for side effects of all concomitant medications regardless of the path of drug elimination.

All concomitant medications must be recorded in the subject's source documentation.

Subjects must be carefully monitored for AEs. This monitoring also includes clinical laboratory tests. Adverse events should be assessed in terms of their seriousness, intensity, and relationship to the study drug, or other chemotherapy/treatment.

6.2.1.1 Definitions

Definition of adverse event (AE)

In a clinical study, an AE is any untoward medical occurrence (i.e. any unfavorable and unintended sign [including abnormal laboratory findings], symptom or disease) in a patient or clinical investigation subject after providing written informed consent for participation in the study. Therefore, an AE may or may not be temporally or causally associated with the use of a medicinal (investigational) product.

A surgical procedure that was planned prior to the start of the study by any physician treating the subject should not be recorded as AE (however, the condition for which the surgery is-required may be an AE if worsens compared to baseline).

- Conditions that started before signing of informed consent and for which no symptoms or treatment are present until signing of informed consent are recorded as medical history (e.g. seasonal allergy without acute complaints).
- Conditions that started before signing of informed consent and for which symptoms or treatment are present after signing of informed consent, at *unchanged intensity*, are recorded as medical history (e.g. allergic pollinosis).
- Conditions that started or deteriorated after signing of informed consent will be documented as adverse events.

Definition of serious adverse event (SAE)

An SAE is classified as any untoward medical occurrence that, at any dose, meets any of the following criteria (a – f):

- a. Results in death.
- b. Is life-threatening.

The term 'life-threatening' in the definition refers to an event in which the patient was at risk of death at the time of the event, it does not refer to an event which hypothetically might have caused death if it were more severe.

- c. Requires inpatient hospitalization or prolongation of existing hospitalization.

A hospitalization or prolongation of hospitalization will not be regarded as an SAE if at least one of the following exceptions is met:

- The admission results in a hospital stay of less than 12 hours.
- The admission is pre-planned.
(i.e. elective or scheduled surgery arranged prior to the start of the study)
- The admission is not associated with an AE.
(e.g. social hospitalization for purposes of respite care).

However, it should be noted that invasive treatment during any hospitalization may fulfill the criterion of 'medically important' and as such may be reportable as an SAE dependent on clinical judgment. In addition, where local regulatory authorities specifically require a more stringent definition, the local regulation takes precedence.

- d. Results in persistent or significant disability / incapacity.

Disability means a substantial disruption of a person's ability to conduct normal life's functions.

- e. Is a congenital anomaly / birth defect.

- f. Is another medically important serious event as judged by the investigator.

6.2.1.2 Classifications for adverse event assessment

All AEs will be assessed and documented by the investigator according to the categories detailed below.

6.2.1.2.1 Seriousness

For each AE, the seriousness must be determined according to the criteria given in Section 6.2.1.1

6.2.1.2.2 Intensity

The intensity of the AE is classified according to the CTCAEv4.0. Grade refers to the severity (intensity) of the AE:

CTCAEv4 Grade 1: mild; asymptomatic or mild symptoms; clinical or diagnostic observations only; intervention is not indicated.

CTCAEv4 Grade 2: moderate; minimal, local, or noninvasive intervention is indicated; limiting to age-appropriate instrumental activities of daily living (ADL; instrumental ADL refers to preparing meals, shopping for groceries or clothes, using the telephone, managing money, etc).

CTCAEv4 Grade 3: Severe or medically significant but not immediately life threatening; hospitalization or prolongation of hospitalization is indicated; disabling;

limiting to self care ADL (self care ADL refers to bathing, dressing and undressing, feeding self, using the toilet, taking medications, and not bedridden).

CTCAEv4 Grade 4: life-threatening consequences; urgent intervention is indicated.

CTCAEv4 Grade 5: death due to an AE.

6.2.1.2.3 Causal relationship

The assessment of the causal relationship between an AE and the administration of treatment is a clinical decision based on all available information.

The causality assessment should be done separately for each study treatment.

The assessment is based on the question whether there was a “reasonable causal relationship” to the study treatment in question.

Possible answers are “yes” or “no”.

An assessment of “no” would include:

1. The existence of a clear alternative explanation, e.g. mechanical bleeding at surgical site.
- or
2. Non-plausibility, e.g. the subject is struck by an automobile when there is no indication that the drug caused disorientation that may have caused the event; cancer developing a few days after the first drug administration.

An assessment of “yes” indicates that there is a reasonable suspicion that the AE is associated with the use of the study treatment.

Factors to be considered in assessing the relationship of the AE to study treatment include:

- The temporal sequence from drug administration: The event should occur after the drug is given. The length of time from drug exposure to event should be evaluated in the clinical context of the event.
- Recovery on drug discontinuation (de-challenge), recurrence on drug re-introduction (re-challenge):
- Subject’s response after de-challenge or subjects response after re-challenge should be considered in the view of the usual clinical course of the event in question.
- Underlying, concomitant, intercurrent diseases:
Each event should be evaluated in the context of the natural history and course of the disease being treated and any other disease the subject may have.
- Concomitant medication or treatment:
The other drugs the subject is taking or the treatment the subject receives should be examined to determine whether any of them may be suspected to cause the event in question.

- The pharmacology and pharmacokinetics of the study treatment:
The pharmacokinetic properties (absorption, distribution, metabolism and excretion) of the study treatment, coupled with the individual subject's pharmacodynamics should be considered.

[Causal relationship to protocol-required procedure(s)]

The assessment of a possible causal relationship between the AE and protocol-required procedure(s) is based on the question whether there was a "reasonable causal relationship" to protocol-required procedure(s).

Possible answers are "yes" or "no".

6.2.1.2.4 Action taken with study treatment

Any action on study treatment to resolve the AE is to be documented using the categories listed below.

The study treatment action should be recorded separately for each study treatment.

- Drug withdrawn
- Drug interrupted
- Dose reduced
- Dose not changed
- Dose increased
- Not applicable
- Unknown

6.2.1.2.5 Other specific treatment(s) of adverse events

- None
- Remedial drug therapy

6.2.1.2.6 Outcome

The outcome of the AE is to be documented as follows:

- Recovered/resolved
- Recovering/resolving
- Recovered/resolved with sequelae
- Not recovered/not resolved
- Fatal
- Unknown

7. CRITERIA FOR EVALUATION AND ENDPOINT ANALYSIS

This study will use the RECIST 1.1 guidelines

7.1 Measurability of Lesions

a. Measurable disease

Measurable disease is defined differently for lymph nodes compared with other disease and will be addressed in a separate section below.

1. Lesions that can be accurately measured in at least one dimension (longest diameter to be recorded) as ≥ 2.0 cm by chest x-ray, by ≥ 1.0 cm with CT or MRI scans, or ≥ 1.0 cm with calipers by clinical exam. All tumor measurements must be recorded in decimal fractions of centimeters (or millimeters).

The defined measurability of lesions on CT scan is based on the assumption that CT slice thickness is 0.5 cm or less. If CT scans have slice thickness greater than 0.5 cm, the minimum size for a measurable lesion should be twice the slice thickness.

2. Malignant lymph nodes are to be considered pathologically enlarged and measurable if it measures ≥ 1.5 cm in **SHORT AXIS** (greatest diameter perpendicular to the long axis of the lymph node) when assessed by scan (CT scan slice recommended being no greater than 0.5 cm).

- b. Non-measurable disease: All other lesions (or sites of disease), including small lesions (longest diameter < 1.0 cm or pathologic lymph nodes with ≥ 1.0 cm to < 1.5 cm short axis), are considered non-measurable disease. Bone lesions, leptomeningeal disease, ascites, pleural/pericardial effusions, lymphangitis cutis/pulmonitis, inflammatory breast disease, and abdominal masses (not followed by CT or MRI), are considered non-measurable as are previously radiated lesions that have not progressed.

c. Notes on measurability

1. For CT and MRIs, the same type of scanner should be used and the image acquisition protocol should be followed as closely as possible to prior scans. Body scans should be performed with breath-hold scanning techniques, if possible.
2. PET-CT: At present, the low dose or attenuation correction CT portion of a PET-CT is not always of optimal diagnostic CT quality for use with RECIST measurements. However, if the site can document that the CT performed as part of a PET-CT is of identical diagnostic quality to a diagnostic CT, then the CT portion of the PET-CT can be used for RECIST measurements and can be used interchangeably with conventional CT.

3. Ultrasound: Ultrasound is not useful in assessment of lesion size and should not be used as a method of measurement.
4. Cystic lesions that meet the criteria for radiographically defined simple cysts should not be considered as malignant lesions (neither measurable nor non-measurable) since they are, by definition simple cysts.
5. If a target lesion becomes very small some radiologists indicate that it is too small to measure. If the lesion is actually still present, a default measurement of 0.5 cm should be applied. If the radiologist believes the lesion has gone, a default measurement of 0.0cm should be

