4.1 Eligibility

4.1.1 Inclusion criteria

- Patients must have histologically or cytologically documented carcinoma primary to the intra- or extra-hepatic biliary system or gall bladder with clinical and/or radiologic evidence of unresectable, locally advanced or metastatic disease. Patients with ampullary carcinoma are not eligible.
- Patients must have failed no more than 2 prior line of systemic chemotherapy for advanced biliary cancer. Patients who received adjuvant chemotherapy and had

evidence of disease recurrence within 6 months of completion of the adjuvant treatment are also eligible. If patient received adjuvant treatment and had disease recurrence after 6 months, patients will only be eligible after failing one line of systemic chemotherapy used to treat the disease recurrence.

- Age \geq 18 years.
- Eastern Cooperative Oncology Group (ECOG) Performance Status Assessment of 0 or 1
- Measurable and non-measurable disease will be allowed.
- Patients must not have been treated with any VEGF inhibitors.
- Life expectancy of at least 12 weeks (3 months).
- For patients who have received prior cryotherapy, radiofrequency ablation, therasphere, ethanol injection, transarterial chemoembolization (TACE) or photodynamic therapy, the following criteria must be met: 28 days have elapsed since that therapy (lesions that have not been treated with local therapy must be present and measurable)
- Subjects must be able to understand and be willing to sign the written informed consent form. A signed informed consent form must be appropriately obtained prior to the conduct of any trial-specific procedure.
- All acute toxic effects of any prior treatment have resolved to NCI-CTCAE v4.0 Grade 1 or less at the time of signing the Informed Consent Form (ICF).
- Adequate bone marrow, liver and liver function as assessed by the following laboratory requirements:
 - Total bilirubin \leq 2.0 x the upper limits of normal (ULN)
 - Alanine aminotransferase (ALT) and aspartate amino-transferase (AST) \leq 2.5 x ULN (\leq 5 x ULN for subjects with liver involvement of their cancer)
 - Alkaline phosphatase limit \leq 2.5 x ULN (\leq 5 x ULN for subjects with liver involvement of their cancer)
 - Serum creatinine \leq 1.5 x the ULN
 - Calculated creatinine clearance $>$ 30 ml/min.
$$\text{Calculated creatinine clearance} = \frac{(140 - \text{age}) \times \text{t (kg)} \times [0.85 \text{ (if female)}]}{72 \times \text{creatinine (mg/dL)}}$$

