7.2 Objective Status at Each Disease Evaluation

Objective Status is to be recorded at each evaluation. All measurable lesions up to a maximum of 2 lesions per organ 5 lesions in total, representative of all involved organs, should be identified as *target* lesions at baseline. All other lesions (or sites of disease) including any measurable lesions over and above the 5 target lesions should be identified as *non-target* lesions. Measurements must be provided for target measurable lesions, while presence or absence must be noted for non-target measurable and non-measurable disease.

For studies that use disease progression as an endpoint, whole body scanning at specific intervals is necessary to determine that progression is NOT present outside of the “target” areas. Therefore, in these studies it is not acceptable to image only the “target” areas of the body in follow-up scans. For study-specific imaging requirements, see the Study Calendar in Section 9.0.

- a. **Complete Response (CR):** Complete disappearance of all target and non-target lesions (with the exception of lymph nodes mentioned below). No new lesions. No disease related symptoms. Any lymph nodes (whether target or non-target) must have reduction in short axis to < 1.0 cm. All disease must be assessed using the same technique as baseline.
- b. **Partial Response (PR):** Applies only to patients with at least one measurable lesion. Greater than or equal to 30% decrease under baseline of the sum of appropriate diameters of all target measurable lesions. No unequivocal progression of non-measurable disease. No new lesions. All target measurable lesions must be assessed using the same techniques as baseline.
- c. **Stable:** Does not qualify for CR, PR, Progression or Symptomatic Deterioration. All target measurable lesions must be assessed using the same techniques as baseline.
- d. **Progression:** One or more of the following must occur: 20% increase in the sum of appropriate diameters of target measurable lesions over smallest sum observed (over baseline if no decrease during therapy) using the same techniques as baseline, as well as an absolute increase of at least 0.5 cm. Unequivocal progression of non-measurable disease in the opinion of the treating physician (an

explanation must be provided). Appearance of any new lesion/site. Death due to disease without prior documentation of progression and without symptomatic deterioration (see Section 10.2e).

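### Sections 7.1b and 7.2 let ablated or embolised lesions serve as target lesions, which can mask growth of untreated tumour in DCR and PFS

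*Combined protocol and SAP*

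**What the plan says.** **Entry (section 4.1.1).** One criterion applies "For patients who have received prior cryotherapy, radiofrequency ablation, therasphere, ethanol injection, transarterial chemoembolization (TACE) or photodynamic therapy". It asks for an interval of 28 days and adds that "lesions that have not been treated with local therapy must be present and measurable". The protocol thus separates treated from untreated lesions at enrolment.

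**Measurability (section 7.1).** Part a defines a measurable non-nodal lesion by accurate measurement and size (1.0 cm or more on CT or MRI), with no condition on prior local therapy. Part b lists small lesions, bone lesions, effusions and other disease, and says that these "are considered non-measurable as are previously radiated lesions that have not progressed". No other kind of pre-treated lesion is named.

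**Target selection (section 7.2).** "All measurable lesions up to a maximum of 2 lesions per organ 5 lesions in total" should be identified as target lesions, representative of the involved organs. No preference for untreated lesions is stated.

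**Progression (section 7.2d).** Measured progression is a "20% increase in the sum of appropriate diameters of target measurable lesions over smallest sum observed", "as well as an absolute increase of at least 0.5 cm". Stable (7.2c) is the residual category.

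**Use (section 8.2).** DCR, defined as CR + PR + SD, and PFS are secondary endpoints. OS at 6 months is primary.

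**The concern.** The eligibility rule requires an untreated measurable lesion, which suggests that treated lesions were not meant to carry the assessment. The assessment rules do not say so. Take a patient with one ablated and one untreated liver lesion, both measurable. The two fit within the limit for one organ, so the written rule puts both in the target sum.

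An ablated or embolised lesion may stay the same size or shrink for reasons unrelated to regorafenib. Its diameter enlarges the baseline sum, so the untreated tumour must grow by more before the sum rises 20%. A patient whose untreated lesion has progressed can then be recorded as Stable, count towards DCR at 8 weeks, and have a later PFS event. In a single-arm trial no comparator shares this error. DCR and PFS are also outcomes in the exploratory biomarker models of section 8.2.

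**Working it through.** The plan states no figure on this point, so there is none to reproduce. The check applies the progression rule of 7.2d to a two-lesion patient.

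**Inputs**
- From 7.2d: a relative threshold of 20% and an absolute threshold of 0.5 cm, both on the sum of target diameters.
- Assumed, not in the documents: a treated lesion T that does not change, an untreated lesion U that grows, baseline as the smallest sum so far (as at the first scan on treatment), and no new lesion.

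**Formulas**
- Growth of U needed with T in the sum: max(0.20 × (T + U), 0.5) / U
- Growth of U needed with T left out: max(0.20 × U, 0.5) / U

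**Results for a range of assumed sizes**

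| T (cm) | U (cm) | T in the sum | T left out |
|---|---|---|---|
| 1.0 | 1.0 | 0.50/1.0 = 50% | 0.50/1.0 = 50% |
| 1.0 | 3.0 | 0.80/3.0 = 26.7% | 0.60/3.0 = 20% |
| 3.0 | 3.0 | 1.20/3.0 = 40% | 0.60/3.0 = 20% |
| 5.0 | 3.0 | 1.60/3.0 = 53.3% | 0.60/3.0 = 20% |
| 3.0 | 2.0 | 1.00/2.0 = 50% | 0.50/2.0 = 25% |
| 5.0 | 2.0 | 1.40/2.0 = 70% | 0.50/2.0 = 25% |
| 4.0 | 1.5 | 1.10/1.5 = 73.3% | 0.50/1.5 = 33.3% |

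The first row shows where the problem vanishes. When T + U is 2.5 cm or less, the 0.5 cm requirement decides in both cases and the treated lesion makes no difference. Above that, dilution rises with T relative to U.

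**One patient worked through (T = 4.0 cm, U from 1.5 to 2.4 cm)**
- Untreated lesion alone: 2.4/1.5 − 1 = +60%, and +0.9 cm. Both thresholds are met, so this is progression.
- Both lesions in the sum: 4.0 + 1.5 = 5.5 cm becomes 4.0 + 2.4 = 6.4 cm, and 6.4/5.5 − 1 = +16.4%. This is below 20%, so the patient is Stable.
- If the treated lesion also shrinks to 3.2 cm: (3.2 + 2.4)/5.5 − 1 = +1.8%. Still Stable.

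**Check on shrinkage read as response.** If T falls from 4.0 to 2.3 cm and U stays at 1.5 cm, the sum changes by 3.8/5.5 − 1 = −30.9%, a PR. Without T the patient is Stable. Both categories count in DCR, so DCR does not move.

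**The case against.** **RECIST 1.1 is adopted by reference.** Section 7 opens by saying that the study will use it, and it may be meant to cover locally treated lesions. The guideline text is not in the documents, so this cannot be settled from them. What stands is that the protocol writes out its own rule, that this rule is narrower than its eligibility wording, and that sites will probably work from the written rule. The same edit serves whether or not the reference was meant to cover the point.

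**Target status is conditional.** This stands. The treated lesion must be large enough, accurately measurable and within the cap. Where an organ has more than two measurable lesions, 7.2 does not force a treated one into a slot. Therasphere might also be argued to count as radiation; the documents do not say.

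**There are other routes out of Stable.** New lesions, unequivocal progression of non-target or non-measurable disease, and symptomatic deterioration all remain. But in the two-lesion case the growing tumour is itself a target, so the route that rests on the physician's opinion about non-target disease does not reach it.

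**Stronger readings to avoid.** A reader might infer that shrinkage of an ablated lesion inflates DCR by creating responders. It does not, because that patient would otherwise be Stable and already counts, and objective response rate is not a listed endpoint. A reader might also multiply a guessed share of locally treated patients by the weight of one patient to get a bias in DCR. The documents give no such share, and having had local therapy is not the same as being misclassified. Nor does the gap touch the primary endpoint, which uses no tumour measurement.

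**Conclusion.** The point holds as a gap between 4.1.1 and sections 7.1b and 7.2. Under the written rules, a qualifying locally treated lesion enters the target sum and can hide growth of untreated tumour. For the assumed sizes above with T + U over 2.5 cm, the growth needed rises from 20–33% to 27–73%; for very small lesions there is no effect.

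The exposure is limited to DCR at 8 weeks and PFS, and the error from masked growth is in the favourable direction. Dilution can also turn a true PR into SD, but that leaves DCR unchanged. As a scale only, one patient among 39 is 1/39 = 2.6 percentage points of DCR. The number affected, and so the total bias, cannot be derived from the documents. OS at 6 months, the sample size and the rule of 16 or more survivors out of 39 are unaffected. The change is worth making because it is cheap and removes a one-directional error from two secondary endpoints, but it does not threaten the trial's main conclusion.

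**What to change.** In 7.1b, replace the clause on radiated lesions with one covering lesions previously treated with radiation, or with any local therapy listed in 4.1.1, that have not progressed since that therapy. In 7.2, state that such lesions are followed as non-target lesions. This also settles how therasphere is handled.

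The cost is small but not nil. Prior local therapy has to be recorded for each lesion at baseline, and judging progression since that therapy needs earlier imaging. The study calendar provides one pre-study scan, so a treated lesion without documented progression should default to non-target. No extra patients or study scans are needed. These patients should still have a target lesion, because 4.1.1 already requires an untreated measurable one.
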